Study Procedures	
The primary objective of this trial is to evaluate the change in serum VEGF-D after 24 weeks of combined resveratrol and sirolimus as compared to the baseline serum VEGF-D value on sirolimus alone. Secondary objectives include an assessment of the safety and tolerability of resveratrol in combination with sirolimus in patients with LAM, as well as the effect of combined resveratrol and sirolimus on lung function and quality of life. The frequency, severity and duration of all adverse events, regardless of cause, will be tabulated by body system and by severity using the NCI Common Terminology Criteria for Adverse Events v4.0. Subjects will have a medical history, physical examination, and laboratory measurements of complete blood count, renal and liver function tests, serum VEGF-D, and sirolimus levels drawn at every in-person visit. Pre and post bronchodilator spirometry measurements will be performed at each visit. St. George's respiratory questionnaire (SGRQ), SD-SB, EuroQOL and ATAQ LAM will be used for quality of life assessment, and these questionnaires will be filled out at each in-person study visit.
 
Patients enrolling in RESULT will be trained on proper technique for home spirometry using an advanced vertical turbine based device that records and wirelessly transmits full flow volumes loops. Once a week, patients will perform at least three spirometry maneuvers that pass ATS/ERS acceptability criteria and choose the best value as their weekly FEV1 and FVC. All spirometric data will be reviewed by an expert pulmonary physiologist, who will judge the spirometry data and loops for intra-test acceptability and reproducibility as specified in the ATS/ERS guidelines, as well as provide near real time electronic feedback to patients regarding their technique. We will correlate spirometry values and trends (absolute as well as rate of decline) obtained from weekly home spirometry with the office-based spirometry values, as well as serum VEGF-D, and quality of life assessment scores.

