### 3.5 Role of home spirometry in pulmonary disorders

In a recent study, 50 patients with idiopathic pulmonary fibrosis (IPF) performed daily home spirometry for a median of 279 days. Office-based spirometry was performed 6- and 12-months after enrollment. In this study, over 80% of the patients adhered to the routine of performing daily spirometry, daily spirometry values showed excellent correlation with office-based spirometry (Figure 11), and the rate of decline in FVC obtained after 3 months of home spirometry was highly predictive of patient outcomes and subsequent mortality (HR: 1.04, CI: 1.02–1.06,  $p<0.001$ ) (Figure 12) (33).

**Figure 11:** Bland-Altman plots demonstrating good agreement between office-based measurements of FEV1 (left) and FVC (right) with home-based measurements. There was a slight bias (0.20 liters) towards consistently higher readings obtained during office-based measurements as opposed to home-based measurements

**Figure 12:** Kaplan-Meier curve demonstrating that the trends obtained from home-based FVC monitoring are predictive of the overall survival in patients with IPF. Left: Increased mortality in patients with FVC decrease more than 5% from baseline after 3 months of monitoring. Right: Increased mortality in patients with FVC decrease more than 10% from baseline after 12 months of monitoring.

Johannson et al. were able to achieve a compliance rate of 90% with once-weekly home spirometry in 24 patients with IPF, and demonstrated that weekly home spirometry is both reliable and feasible in this patient population. Addition of weekly home spirometry resulted in enhanced precision, and was estimated to reduce the sample size needed to study the efficacy of a new intervention by four-fold (34). In another recent study, patients with cystic fibrosis randomized to twice-weekly home spirometry measurements had a statistically significant shorter time to detection of disease-related exacerbations as opposed to usual care. However, the adherence to home spirometry in this study was suboptimal with 50% of the population consistently performing once-weekly testing, and only 19% of the population adhering to the twice-weekly regimen (35). Home spirometry has been shown to facilitate early detection of bronchiolitis obliterans following lung transplantation as compared to office-based spirometry (36, 37).

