### **4.2 Secondary Endpoints:**

1. Safety and adverse effect profile of combined resveratrol and sirolimus in patients with LAM
2. Mean change in FEV1 before and after treatment
3. Mean change in FVC before and after treatment
4. Difference in rate of change in FVC (slope) before and after treatment
5. Difference in rate of change in FEV1 (slope) before and after treatment
6. Mean change in diffusion capacity of carbon monoxide (DLCO) before and after treatment
7. Difference in rate of change in DLCO (slope) before and after treatment
8. Baseline to 24-week change in the score on St. George's Respiratory Questionnaire (SGRQ)
9. Baseline to 24-week change in the score on ATAQ-LAM (A tool to assess quality of life in LAM)
10. Baseline to 24-week change in the score on SD-SOB score (San Diego Shortness of Breath Questionnaire)
11. Baseline to 24-week change in the score on EuroQOL scale
12. Overall compliance with weekly home spirometry.
13. Correlation between home spirometry values (absolute as well as trends) with office-based spirometry values and trends.

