### **5.2 Inclusion Criteria:**

Subjects enrolled in the trial must meet **all** of the following criteria.

1. Definitive diagnosis LAM based on the presence of characteristic cystic change on high-resolution computed tomography (HRCT) of the chest. The diagnosis must be confirmed by one of the following:
  - A) Histopathological confirmation by biopsy (lung, abdominal mass, lymph node or kidney or cytology from thoracic or abdominal sources revealing HMB45+ staining of spindled/epithelioid cells)
  - B) Compatible chest CT scan findings in the setting of tuberous sclerosis, angiomyolipomas (diagnosed by CT, MRI by the site radiologist or biopsy) or chylous pleural effusion (verified by tap)
  - C) Chest CT scan findings compatible with LAM and a VEGF-D level  $\geq$  800pg/ml.
2. Age 18 years or greater
3. Signed and dated informed consent
4. Currently on sirolimus for treatment of LAM for at least 20 weeks
5. Evidence of disease stabilization on sirolimus as demonstrated by two stable values of serum VEGF-D post initiation of sirolimus drawn at least 12 weeks apart from each other. For the purpose of this study, a variation in serum VEGF-D of less than or equal to 15% is considered stable.

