## 6. Study Procedures and Timelines

### 6.1 Study and Timeline Overview

Patients will be identified by the medical and research staff at the LAM clinic at the University of Cincinnati Medical Center. Study staff will screen up to 60 patients over 15 months with a goal of enrolling 25 participants. Patients who meet eligibility criteria, provide informed consent and are enrolled in the study will receive instructions regarding resveratrol dosage, route and administration. An 8-week supply of resveratrol will be provided at visit 1. Patients will begin resveratrol at a starting dose of 250mg daily, and increase the dose in two increments to a maximum dose of 1000mg daily. If patients do not tolerate a certain dose of resveratrol, the dose will be reduced to the last tolerated strength. Patients will remain on the last well-tolerated dose of resveratrol for the entire study duration. Patients who are unable to tolerate the lowest dose of resveratrol will be withdrawn from study.

The patients will be given a copy of the informed consent form. Patients will be given ample time to read and discuss the consent form with the study staff. The study staff will then answer any remaining questions asked by the patients. The patients will be offered the option of signing the consent form. Those who agree to participate will undergo the remainder of screening visit.

Prior to starting study drug, pre/post bronchodilator spirometry, diffusion capacity of carbon monoxide (DLCO), and serum VEGF-D will be obtained to establish baseline values prior to study drug initiation. The best values for FEV1 and FVC obtained during the spirometry maneuvers will be used. Patients will be followed with serial spirometry and VEGF-D levels collected at the initial visit, followed by week 8, week 16 and week 24 visits. DLCO will also be obtained at the 24-week visit in addition to spirometry.

For patients who agree to the home spirometry study, we will teach them on the proper technique to perform, record and transmit home spirometry, and provide them with a home spirometer. The patients will perform their first test during the initial visit and we will use those values to compare the home spirometer values with the office-based spirometry values. After that patients will be instructed to perform home spirometry once a week as detailed in Section 5.7.

Section 6.2 provides a summary of the study timeline and procedures.

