**Home spirometry evaluation:** The spirometry values will be expressed as mean  $\pm$  SD. All spirometry maneuvers will be checked for acceptability and reproducibility as specified in the ATS/ERS criteria (38) by an expert pulmonary physiologist. The spirometry values obtained from maneuvers that do not satisfy the ATS/ERS criteria for acceptability will not be used in the primary analysis. If spirometric values meet the acceptability criteria but fail to satisfy the repeatability criteria, those values will be graded for quality, but will be used in the primary analysis. Overall compliance with weekly home spirometry will be recorded and reported as a percentage. Comparison of home spirometry and office-based spirometry values will be performed using the Bland-Altman method at baseline, and at each time frame that patients get an office-based spirometry (i.e. every 8 weeks). Rate of change of FEV1 (slope) over time will be calculated by using all available values (without imputations) in a linear mixed effects model after considering the correlation of the observations within each subject, and the time between measurements will be treated as a fixed effect. In order to analyze if the trends obtained from short-term follow up with frequent home spirometry correlate with overall disease trajectory, we will compare the rate of decline obtained after 8 weeks of home spirometry to the overall rate of decline obtained after 24 weeks of follow up. A similar analysis plan will be employed for serum VEGF-D, and other biomarkers. All statistical analyses for this study will be performed using SAS, version 9.4 (SAS Institute Cary NC).

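### Secondary endpoint 13 words home-versus-office spirometry as correlation, while the analysis section plans Bland-Altman for values and names no agreement analysis for home against office slopes

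*Combined protocol and SAP*

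**What the plan says.** Endpoint 13 in Section 4.2 reads "Correlation between home spirometry values (absolute as well as trends) with office-based spirometry values and trends". The synopsis (Study Procedures) repeats the metric: "We will correlate spirometry values and trends (absolute as well as rate of decline) obtained from weekly home spirometry with the office-based spirometry values".

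The analysis text, in Section 15 and in the synopsis under Data Analysis, is different. For values it says "Comparison of home spirometry and office-based spirometry values will be performed using the Bland-Altman method at baseline", and it repeats this at each office visit, every 8 weeks. Section 6.1 adds a same-visit check with the patient's first home-device test: "we will use those values to compare the home spirometer values with the office-based spirometry values".

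For trends, Section 15 estimates the FEV1 slope in a linear mixed model and then says "we will compare the rate of decline obtained after 8 weeks of home spirometry to the overall rate of decline obtained after 24 weeks". It does not say which device supplies the 24-week rate.

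The only overall success threshold for home spirometry is more than 80% compliance (Section 5.7). No acceptable bias, limit of agreement or slope difference is stated. Section 3.6 says that the project will validate home spirometry as a monitoring tool, whereas the synopsis objective is feasibility and reliability.

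**The concern.** Correlation measures how well one device ranks patients relative to the other. It does not measure whether the two give the same answer.

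- **Values.** Adding a constant to every home reading leaves the coefficient unchanged. Such an offset is realistic: for the cited study in idiopathic pulmonary fibrosis, Section 3.5 reports "There was a slight bias (0.20 liters) towards consistently higher readings obtained during office-based measurements".
- **Trends.** The coefficient rises with the spread of true slopes between patients and falls with measurement noise. With little spread in true slopes, a sound device gives a low coefficient; with wide spread, the same device gives a higher one.

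The 8-week against 24-week comparison does not fill the gap. It asks whether an early rate predicts the later one, over different time windows, and not whether home and office slopes agree over the same period.

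What is at stake is how endpoint 13 is read. A high value correlation could be reported as support for the device despite an offset, and a low trend correlation could be reported as failure when it reflects the patients and the visit schedule.

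**Working it through.** The plan gives no power, target correlation or agreement limit for endpoint 13, so there is no stated figure to reproduce. It also gives no spirometry SDs, so every SD below is an assumption shown as a range.

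**Values.** With between-patient variance Vb and within-patient variance Ve, equal for both devices, r = Vb/(Vb + Ve). The bias does not appear in the formula.

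- Between-patient SD 0.5 L, within-patient SD 0.15 L: 0.25/(0.25 + 0.0225) = 0.92.
- Between-patient SD 0.9 L, within-patient SD 0.05 L: 0.81/(0.81 + 0.0025) = 0.997.
- The concordance coefficient, 2Vb/[2(Vb + Ve) + bias²], does respond to bias. At 0.20 L it is 0.86 and 0.97 for these two cases.
- With less spread and more noise r is lower: 0.80 at SDs of 0.3 and 0.15 L, and 0.59 at 0.3 and 0.25 L.

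**What the planned Bland-Altman analysis delivers.** Assume one pair per patient, n = 20 (the evaluable target) and within-patient SD of 0.05 to 0.15 L per device. The SD of a difference is √2 times that. The 95% CI for bias is ±0.03 to ±0.10 L, and for each limit of agreement ±0.06 to ±0.17 L. A 0.20 L bias would be detected with about 98% power or more.

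**Trends.** The slope SE is (error SD/√Sxx) × 52, in ml/year.

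- Office, weeks 0, 8, 16 and 24: Sxx = 144 + 16 + 16 + 144 = 320. Error SD of 60 to 100 ml gives SE 174 to 291.
- Home, 25 weekly readings: Sxx = 25 × (25² − 1)/12 = 1300. Error SD of 80 to 150 ml gives SE 115 to 216.

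For a device with no slope error of its own and true-slope SD τ, expected r = τ²/√[(τ² + SEo²)(τ² + SEh²)]:

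| τ (ml/year) | Lower noise (SE 174, 115) | Higher noise (SE 291, 216) |
|---|---|---|
| 25 | 0.03 | 0.01 |
| 100 | 0.33 | 0.14 |
| 200 | 0.65 | 0.38 |
| 300 | 0.81 | 0.58 |

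For τ of 25 to 100 ml/year, the chance of a two-sided p below 0.05 by Fisher's z at n = 22 is 5 to 31%. The figure of 22 is an assumption between the 20 evaluable and 25 enrolled; uptake of the substudy is not stated. At n = 20 the 95% CI around r = 0.2 is −0.27 to 0.59.

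**Slope difference from the same data.** If true home and office slopes are equal within each patient, the SD of one patient's observed difference is √(174² + 115²) = 209 to √(291² + 216²) = 362 ml/year. Dividing by √22 gives an SE of 45 to 77 ml/year. With t = 2.08 (21 df) the 95% CI is about ±93 to ±161 ml/year. Raw limits of agreement for individual slope differences would be 1.96 × 209 = ±410 to 1.96 × 362 = ±710 ml/year from measurement noise alone.

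**The case against.** Much of the opposing case stands.

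- **Values are covered in substance.** Bland-Altman at four visits, plus the same-visit check, would show an offset of 0.20 L. A reader might infer from endpoint 13 that the trial cannot establish whether the device is valid. The documents do not support that: for values the defect is a mismatch between endpoint and analysis. Nor do they call 0.20 L clinically large; Section 3.5 describes it as slight.
- **Trends are partly covered.** A home-minus-office difference that stays constant over weeks 0, 8, 16 and 24 implies that the mean trends agree. Even so, no slope contrast is named and none would be reported with an interval.
- **A low trend correlation is not a foregone conclusion.** A reader might infer that it must be near zero because all patients are stabilized. Inclusion criterion 5, "Evidence of disease stabilization on sirolimus", is judged on serum VEGF-D and has no FEV1 requirement. Section 3.2 describes lung-function stabilization on sirolimus for the group, while Section 3.3 reports that individual FEV1 responses varied. The small true-slope SDs are assumptions, and at 200 to 300 ml/year the coefficient is moderate to high.
- **A mean slope difference has its own blind spot.** If the average slope is near zero, a device insensitive to change would also average near zero and would appear to agree. The spread of the differences must therefore be reported too.
- **Stakes are low.** This is the last of 13 secondary endpoints, in an opt-in substudy of an exploratory phase II trial, and nothing is powered on it.

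None of this makes correlation a measure of agreement. Its size still depends on patient spread, and it still ignores a constant offset.

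**Conclusion.** The point holds as a minor one. Endpoint 13 is worded as correlation, does not match the Bland-Altman analysis planned for values, and leaves home-against-office slope agreement without a named analysis.

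For values, a bias of any size leaves the coefficient unchanged (0.92 to 0.997 under the main assumed SDs), but the planned analysis would reveal it. For trends, a sound device would be expected to give r of about 0.01 to 0.33 at a true-slope SD of 25 to 100 ml/year, and about 0.4 to 0.8 at 200 to 300 ml/year. These figures rest on assumed SDs, independent errors, complete weekly data and equal true slopes on both devices. The conclusion that correlation cannot separate device quality from patient spread does not depend on them. The primary endpoint is unaffected.

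**What to change.** Restate endpoint 13 as agreement, in Section 4.2, the synopsis and Section 15.

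- **Values:** the mean home-office difference and limits of agreement from the Bland-Altman analysis already planned.
- **Trends:** the home-minus-office slope difference with 95% CI, from one mixed model with method, time and method-by-time, and patient random intercepts and slopes by method. Report also the between-patient SD, or limits of agreement, of the slope differences, since the mean alone cannot show whether individual patients are tracked. Raw limits need to be read against the noise-only width shown above.
- **Correlations:** keep as description only.

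If an acceptable difference is to be applied, it should be written down before the data are examined.

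The cost is wording and a little more analysis, with no new visits or measurements. The slope interval will be wide, about ±90 to ±160 ml/year at 22 patients and wider if fewer opt in. With four office points per patient, the random slopes by method may be poorly estimated; differences of per-patient fitted slopes would be a simple fallback.

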## **5. Study Design:**

This is an open label, non-randomized, dose-escalation study conducted as a phase II safety and efficacy study. Patients will continue on their existing background therapy of sirolimus for treatment of LAM.

### **5.1 Identification and Screening:**

Potential participants will be identified through the University of Cincinnati Medical Center LAM Clinic, which provides clinical care for patients with LAM. LAM patients may also learn of the study from the LAM Foundation web site or the study listing on ClinicalTrials.gov. Potential study participants will be screened for eligibility. Study staff expects to screen the required sample size of 25 patients over a 15-month time frame. Potential participants will be informed about the study, and following completion of the informed consent process, a screening evaluation will be performed. Informed consent will be obtained *before* any study procedures are performed. Informed consent for participation in this study may be obtained in-person or remotely via telephone.

### **5.2 Inclusion Criteria:**

Subjects enrolled in the trial must meet **all** of the following criteria.

1. Definitive diagnosis LAM based on the presence of characteristic cystic change on high-resolution computed tomography (HRCT) of the chest. The diagnosis must be confirmed by one of the following:
  - A) Histopathological confirmation by biopsy (lung, abdominal mass, lymph node or kidney or cytology from thoracic or abdominal sources revealing HMB45+ staining of spindled/epithelioid cells)
  - B) Compatible chest CT scan findings in the setting of tuberous sclerosis, angiomyolipomas (diagnosed by CT, MRI by the site radiologist or biopsy) or chylous pleural effusion (verified by tap)
  - C) Chest CT scan findings compatible with LAM and a VEGF-D level  $\geq$  800pg/ml.
2. Age 18 years or greater
3. Signed and dated informed consent
4. Currently on sirolimus for treatment of LAM for at least 20 weeks
5. Evidence of disease stabilization on sirolimus as demonstrated by two stable values of serum VEGF-D post initiation of sirolimus drawn at least 12 weeks apart from each other. For the purpose of this study, a variation in serum VEGF-D of less than or equal to 15% is considered stable.

### **5.3 Exclusion Criteria:**

Subjects who meet **any** of the following criteria are not eligible for enrollment as study participants:

1. Known allergy or hypersensitivity to resveratrol
2. Inability to provide informed consent
3. Active enrollment in other clinical drug trials for LAM
4. Pregnant or plan to become pregnant in the next 6 months
5. Breast feeding
6. Inability to comply with pulmonary function tests or follow up visits
7. Inadequate contraception
8. Use of estrogen containing medications within the 30 days prior to randomization
9. History of organ transplant
10. Actively listed for lung transplantation
11. Inability to comply with study procedures or attend scheduled study visits
12. Any clinically significant medical disease (other than LAM) that is associated with an expected survival of less than 2 years, or likely to impact the ability of the patient to participate in the study in the opinion of the investigator, or impact the study efficacy or safety assessments.
13. Concomitant use of resveratrol with drugs with a narrow therapeutic range that are CYP3A, CYP1A2, CYP2D6, or CYP2C9 substrates (for example, theophylline, tizanidine, warfarin, phenytoin, alfentanil, dihydroergotamine, ergotamine, fentanyl, pimozide, quinidine, cyclosporine, tacrolimus, thioridazine) will be prohibited from Day 1 until the end of study.

#### **5.4 Recruitment:**

Patients will be recruited from The University of Cincinnati Medical Center LAM Clinic, and referred by physicians and LAM support groups such as the LAM Foundation, and the Tuberous Sclerosis Alliance. IRB approved recruitment materials may be posted in public places such as LAM clinics, The LAM Foundation, the Tuberous Sclerosis Alliance, LAM patient and/or physician events, conferences and websites. The study will be posted on clinicaltrials.gov.

Potential study participants will be contacted by the study staff to determine interest in study participation. Contact may be made by mail, electronic mail, telephone or in person. Interested individuals will receive study information, including a cover letter and a consent form. Informed consent for study participation may be obtained in-person or over the phone.

